Study Protocol

Official Title: Telemedicine for Reach, Education, Access, and Treatment-Ongoing (Treat-On) Study

ClinicalTrials.gov ID (NCT number): NCT04107935

Document Date: 7-24-23

Study Protocol

This was a 12-month non-randomized trial that evaluated TREAT-ON prospectively and compared it to a retrospective in-person diabetes self-management education and support (DSMES) program. Both programs were offered at Federally Qualified Health Centers (FQHCs) providing care to mostly medically underserved, underinsured and uninsured in rural communities located across three of the most distressed counties in Western Pennsylvania. The University of Pittsburgh Medical Center (UPMC) services extend across the region, and based on UPMC Health Plan data, approximately 1,300 adult patient-members with T2DM received care at the participating FQHCs (58% female, mean age 58y, >75% Medicare/Medicaid) at the time of the study. The FQHCs were chosen because they offered the UPMC Health Plan's *Diabetes High Risk Initiative*, an insurer-based DSMES program, to patient-members with a diagnosis of T2DM and considered to be at "high risk" for diabetes-related problems (Zupa et al, 2019). The purpose of this study was to compare TREAT-ON, an enhanced telehealth version of the *Diabetes High Risk Initiative*, to matched controls who had already completed the *Diabetes High Risk Initiative* in person. This study was approved by the University of Pittsburgh's Institutional Review Board.

Models for DSMES

The original Diabetes High Risk Program: The Diabetes Care and Education Specialist (DCES)-driven *Diabetes High Risk Initiative* (Zupa et al, 2019) was designed to address key components that have been shown to improve quality outcomes in primary care that include, population health, self-management, and coordinated team care (Wagner et al, 1996). A DCES proactively identified high risk patient members and provided in-person DSMES. Patients were identified through the insurer's population health reports, which are routinely generated and reviewed to allow for proactive identification of individuals who may benefit from supplemented chronic care management. The DCES created a referral for DSMES to patients considered to be at high risk for diabetes-related problems who met the following criteria: diabetes-related emergency room visit or hospitalization, HbA1c >9%, and reported barriers to care. Barriers to care included lack of access to care because of transportation problems, cost barriers due to difficulty in affording medications and supplies, and challenges with comprehension of a care plan due to deficits in knowledge about diabetes or general health literacy. Treatment ranged from chart review and plan of care with medication recommendations to the primary care provider (PCP) to telephone-based or in-person individualized DSMES sessions with patients, depending on patient needs and preferences. The DSMES sessions were in keeping with the assessment and content presented in the National Standards for DSMES (Davis et al, 2022).

The TREAT-ON Model: TREAT-ON (Figure) is an enhancement of the *Diabetes High Risk Initiative* with the addition of real-time telemedicine videoconferencing to allow remote access to self-management support within the privacy of a patient's home (or location of their choosing). Recognizing that rural communities experience challenges with internet connectivity that could preclude participation, we learned that 96.5% of the population in the area, where the study was conducted, was reported to have broadband connectivity.

The DSMES intervention was initiated by the DCES where a comprehensive assessment (review of clinical needs, history, psychosocial needs and barriers, current therapy, nutrition, activity, risk factors, coping strategies, problem solving skills, with attention to health literacy and cultural influences) was conducted. Based on the assessment, the DCES collaborated with the patient (and PCP) to establish an individualized treatment plan with medication recommendations and self-management goal(s), as well as provide DSMES. Building on this, ongoing management and support was delivered to the patient (and their caregiver if invited) via

videoconferencing. As part of ongoing support, the DCES was available upon need and request to the patient over the 12-month period, the DCES had the opportunity to assess an individual's progress towards meeting their self-management goals, address challenges and barriers that may be impeding progress, and reinforce self-care behaviors, problem solving-skills and coping strategies. Consistent with the patient empowerment-oriented approach, a patient-centered model tailored to meet the patient's needs (Anderson et al, 1995) the DCES collaborated with the patient to determine content for discussion, number, length and frequency of follow-up sessions. Content was in keeping with the National Standards for DSMES (Davis et al, 2022).

Recruitment, Enrollment and Training

Study patient participants were identified through the UPMC Health Plan population health reports and were invited to participate by a DCES at a participating FQHC if the individual met the "high risk" conditions (Zupa et al, 2019). Participating patients were consented and introduced to the TREAT-ON model and familiarized with the telemedicine videoconferencing technology by the DCES and health system's technology staff.

Outcome Measures

Data were collected at baseline and 3, 6 and 12 months for all outcome measures except for intervention acceptability, which was only assessed at follow-up. HbA1c served as the primary outcome and clinical measure of improved DM management. HbA1c values were obtained from the patient's medical record. Behavioral and psychosocial outcomes were assessed with validated self-report instruments.

[figure not shown]

Figure. Overview of TREAT-ON Model of Care

References

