Statistical Analysis Plan

Official Title: Telemedicine for Reach, Education, Access, and Treatment- Ongoing (Treat-On) Study

ClinicalTrials.gov ID (NCT number): NCT04107935

Document Date: 7-24-23

Statistical Analysis

We expected to enroll 50 participants into the intervention and compare to a retrospective usual care group (control) that was also anticipated to include 50 participants. Control participants were identified from a pre-existing data set.

A control group was selected from individuals who had previously participated in the *Diabetes High Risk Initiative*. Propensity score matching was used to form pairs of intervention and control participants. Specifically, a greedy matching procedure with a matching caliper of 0.2 of the standard deviation of the logit of the propensity score was used to create pairs. For a participant in the intervention group, the closest control participant within the specified caliper distance was selected for matching. Factors selected *a priori* for inclusion in the propensity score included several covariates known to be possible correlates of HbA1c: race (White and non-white), ethnicity, age, body mass index (BMI), baseline HbA1c, and gender. Standardized mean differences were then calculated to examine the balance between the two exposure groups. Variables with standard mean differences <0.1 were considered to be balanced.

Baseline characteristics of the intervention and control group as well as those who met and did not meet their diabetes self-management goal were presented using measures of central tendency (median, interquartile range) for continuous variables and number and percentage for categorical variables. Comparisons were made using the Wilcoxon rank sum and chi-sq tests. To examine the change in HbA1c over time, mixed model regression was employed. Since the baseline characteristics achieved a good balance, those variables were not entered into the propensity score matched model.

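### Protocol and SAP describe the control pool differently: taken literally, the Protocol selects controls on completion, while the SAP wording does not support the in-person label

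*Protocol*

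**What the plan says.** **Control pool.** The opening section of the Protocol gives the comparator as "matched controls who had already completed the" Initiative in person. The SAP, under Statistical Analysis, states that "Control participants were identified from a pre-existing data set" and that "A control group was selected from individuals who had previously participated in the" Initiative. The SAP mentions neither completion nor mode of delivery as a condition. Neither document defines completion.

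**What the Initiative delivered.** Under Models for DSMES, the Protocol first says "A DCES proactively identified high risk patient members and provided in-person DSMES". The same paragraph then says "Treatment ranged from chart review and plan of care with medication recommendations to the primary care provider (PCP) to telephone-based" or in-person sessions, according to what the patient needed and preferred.

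**Entry to TREAT-ON.** Under Recruitment, Enrollment and Training, patients found through the insurer's reports "were invited to participate by a DCES at a participating FQHC if the individual met the" high-risk conditions, and then gave consent. In the TREAT-ON model "the DCES collaborated with the patient to determine content for discussion, number, length and frequency of follow-up sessions", so there is no fixed course to complete.

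**Adjustment.** The propensity score uses age, gender, race, ethnicity, BMI and baseline HbA1c. The matched mixed model for HbA1c, the primary outcome, has no further baseline covariates.

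**The concern.** The control pool is one side of the primary comparison, and a reader cannot tell from the two documents which records were eligible for it. People who completed a programme are a subset of those who took part, and completion is known only after baseline. If it was required of controls and not of TREAT-ON participants, the groups differ by a selection that has nothing to do with telehealth. If completers do better on HbA1c, that mechanism alone makes the control group look better.

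The SAP wording avoids this problem but raises another. A pool of everyone who took part can include people managed by chart review or telephone only. Telehealth against in-person education is the stated contrast, so the comparator's delivery mode determines what the trial can conclude.

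**Working it through.** There is no figure in the plan to reproduce. The SAP expects 50 participants per group and gives no effect size, standard deviation or power. The check is a comparison of the texts, followed by an illustration.

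**Step 1: the two definitions side by side.**
- Protocol wording, taken literally: completed, and in person. Both conditions restrict the pool.
- SAP wording: took part. Neither condition appears.
- The wordings are compatible only if the Protocol phrase is a loose way of saying that the programme was in the past and the in-person label is also loose.

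**Step 2: is there a matching condition in the TREAT-ON group?** Entry rested on high-risk status, care at a participating centre, invitation and consent. All of these precede the intervention, and none depends on later attendance. A completion filter would therefore apply to controls only.

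**Step 3: would the matching deal with it?** None of the six propensity variables measures engagement or attendance. Matching can remove the part of a completer difference that those variables explain. It cannot be relied on to remove the rest, and the matched model adds nothing that would.

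**Step 4: illustrative size.** Both inputs are assumptions; neither is in the documents.
- c = share of control-programme starters who complete, assumed 0.6 to 0.8.
- g = completers' mean HbA1c improvement minus non-completers', remaining after matching, assumed 0.5 to 1.0 points.

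Let the mean improvement be m among completers and m - g among non-completers.
- All starters: c x m + (1 - c) x (m - g) = m - (1 - c) x g.
- Completers only: m.
- Shift from a control-only filter: (1 - c) x g, favouring controls.

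Results with g = 0.5:
- c = 0.8: 0.2 x 0.5 = 0.10
- c = 0.7: 0.3 x 0.5 = 0.15
- c = 0.6: 0.4 x 0.5 = 0.20

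Results with g = 1.0:
- c = 0.8: 0.2 x 1.0 = 0.20
- c = 0.7: 0.3 x 1.0 = 0.30
- c = 0.6: 0.4 x 1.0 = 0.40

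Without a filter the shift is 0.

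**Step 5: delivery mode.** This step needs no assumption about completion. The Protocol's description of the Initiative allows care without any in-person session, and the SAP does not exclude such people from the pool.

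**The case against.** The best reply is that the Protocol phrase stands in a statement of purpose, not in a selection rule. The same section contrasts a prospective group with a retrospective one, so the phrase reads naturally as a remark about time. The text that does describe selection is in the SAP and sets no completion condition. The Initiative also had no fixed number of sessions or end point, so a completion filter could not be identified from the documents even if one was intended. All of this stands. It shows that the loose reading is plausible, but it does not settle which records were used, and it leaves the in-person label unsupported.

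Two stronger readings are tempting. A reader might infer that controls were in fact restricted to completers and that the HbA1c comparison is therefore biased against TREAT-ON. The documents show no such filter. TREAT-ON participants were themselves invited and consenting, which is a selection of its own, so even the net direction is open.

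A reader might also set "We expected to enroll 50 participants into the intervention" beside the 42 in the SAP's secondary analysis and infer that eight people were dropped for not completing. The 50 is an expectation. The SAP does not say that 50 enrolled or why the number is 42. Attrition in the intervention group would in any case be a separate question.

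**Conclusion.** The point holds as an inconsistency in the definition of the comparator, and it should be resolved. It is not evidence of a demonstrated bias. Each wording leaves a different problem: the literal Protocol wording conditions controls alone on a later event, and the SAP wording leaves the contrast with in-person care without support. The 0.10-0.40 range is conditional on a filter having been used and on both assumed inputs, so it shows a possible order of size and is not an estimate. Only the sponsor can say which records were eligible.

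**What to change.** - **One control pool in both documents.** The pool eligible for matching is everyone in the pre-existing data set who started the Initiative and met the high-risk criteria that the Protocol already lists, whether or not they completed it. Matched controls are then drawn from that pool as the SAP describes.
- **One time origin.** State a programme-start date that can be identified in both groups, including for controls whose care was chart review. Count baseline and the 3-, 6- and 12-month HbA1c values from it.
- **Comparator label.** Call the comparator in-person only if the selected controls had in-person sessions. Otherwise describe it as the Initiative as delivered.
- **If completers were in fact used.** Draw the controls again from the same data set under the start-based rule, and rerun the match and the mixed model.

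The cost is wording in both documents. The new draw and rerun arise only if a completion filter was applied, and they need no additional patients.

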Statistical Analysis Plan

Official Title: Telemedicine for Reach, Education, Access, and Treatment- Ongoing (Treat-On) Study

ClinicalTrials.gov ID (NCT number): NCT04107935

Document Date: 7-24-23

Statistical Analysis

We expected to enroll 50 participants into the intervention and compare to a retrospective usual care group (control) that was also anticipated to include 50 participants. Control participants were identified from a pre-existing data set.

A control group was selected from individuals who had previously participated in the *Diabetes High Risk Initiative*. Propensity score matching was used to form pairs of intervention and control participants. Specifically, a greedy matching procedure with a matching caliper of 0.2 of the standard deviation of the logit of the propensity score was used to create pairs. For a participant in the intervention group, the closest control participant within the specified caliper distance was selected for matching. Factors selected *a priori* for inclusion in the propensity score included several covariates known to be possible correlates of HbA1c: race (White and non-white), ethnicity, age, body mass index (BMI), baseline HbA1c, and gender. Standardized mean differences were then calculated to examine the balance between the two exposure groups. Variables with standard mean differences <0.1 were considered to be balanced.

Baseline characteristics of the intervention and control group as well as those who met and did not meet their diabetes self-management goal were presented using measures of central tendency (median, interquartile range) for continuous variables and number and percentage for categorical variables. Comparisons were made using the Wilcoxon rank sum and chi-sq tests. To examine the change in HbA1c over time, mixed model regression was employed. Since the baseline characteristics achieved a good balance, those variables were not entered into the propensity score matched model.

A secondary analysis, using only the participants in the intervention group (n=42), was performed to examine the difference in HbA1c and survey scores for self-care, diabetes distress, empowerment, and the TUQ between those that met their diabetes self-management goal versus those that did not. Similar analyses methods were used except the mixed models were adjusted for age, race, BMI, gender. P-values <0.05 was considered significant. Finally, acceptability and feasibility of the intervention were examined at the end of the study (at month 12) using descriptive statistics. All analyses were carried out using SAS 9.4 (Carey Institute Inc).

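### Controls come from an earlier programme period and both programmes recommend medication, but baseline glucose-lowering regimen is not among the matching factors, so the HbA1c contrast is open to confounding by background therapy and period.

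*SAP*

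**What the plan says.** The opening paragraph of the Protocol sets out the design: "This was a 12-month non-randomized trial that evaluated TREAT-ON prospectively and compared it to a retrospective in-person diabetes self-management education and support (DSMES) program". It describes the comparison group as "matched controls who had already completed the" Diabetes High Risk Initiative in person. The SAP, under Statistical Analysis, expects 50 intervention participants and plans to "compare to a retrospective usual care group (control) that was also anticipated to include 50 participants". It agrees on timing: "A control group was selected from individuals who had previously participated in the" same initiative, and "Control participants were identified from a pre-existing data set". Neither document gives calendar dates for either group.

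Medication is part of both programmes. Under Models for DSMES, the original programme could include a "plan of care with medication recommendations to the primary care provider (PCP"), and in TREAT-ON the educator worked with the patient and PCP to "establish an individualized treatment plan with medication recommendations and self-management goal(s"). The Protocol also counts difficulty in affording medications among the barriers that define a high-risk patient.

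The propensity score in the SAP has six factors: race, ethnicity, age, BMI, baseline HbA1c and gender. A standardised mean difference below 0.1 counts as balance. Because balance was judged good, those factors are left out of the matched mixed model, and no other covariate is described for it.

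**The concern.** A prospective arm compared with past participants ties arm to calendar period. That matters here because the primary outcome is HbA1c and medication is one of the routes by which either programme can change it. The result for a given patient depends partly on the regimen at entry and on what could be added at the time.

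Take two patients with the same HbA1c above 9%, one on a single oral agent and the other on insulin plus several agents. The matching treats them as equivalent if the other five factors agree, yet they differ in how much room is left to intensify treatment. The SAP says that it chose factors thought to correlate with HbA1c. Background glucose-lowering therapy meets that criterion and is not on the list.

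At stake is the interpretation of the main comparison. A difference between arms, or the lack of one, could reflect regimen at entry or period rather than the mode of delivery. The balance check would not reveal this, because it covers only the factors in the score.

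**Working it through.** **1. Which variables the plan controls**

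| Variable | Propensity score | Matched mixed model | Secondary model (intervention group only) |
|---|---|---|---|
| Age, race, BMI, gender | yes | no | yes |
| Ethnicity, baseline HbA1c | yes | no | not listed |
| Baseline glucose-lowering regimen | not listed | not listed | not listed |
| Calendar date | not listed | not listed | not listed |

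No sensitivity analysis for time trends or unmeasured confounding is described. The secondary model compares TREAT-ON participants with one another, so it cannot help the between-arm contrast.

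**2. What the matched contrast estimates**

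Write the between-arm difference in HbA1c change as

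D = T + P + g × r

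Here T is the programme effect and P is the effect of period. The term r is the difference between arms in baseline regimen that remains after matching on the six factors, and g is the effect of that regimen difference on HbA1c change. Matching on baseline HbA1c does not force r to zero, because the same HbA1c can arise under different regimens. Adding regimen to the score addresses g × r. It does not remove P. If the two calendar windows do not overlap, date coincides with arm and can be neither matched nor adjusted for.

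**3. Can the size be computed?**

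No. The documents give no regimen data, no dates and no SD of HbA1c change. The 50 per group cannot be reproduced either, since no effect size, SD, power or sidedness accompanies it.

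**4. Illustration on assumed inputs**

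Let b be the total bias in HbA1c points (P + g × r). Assume a two-sided 5% test, a single-time-point contrast, SD of change 1.5 to 2.5, and no allowance for pair correlation. Then SE = SD × √(2/n). With no true programme effect,

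P(significant) = P(Z > 1.96 − b/SE) + P(Z < −1.96 − b/SE).

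For b, suppose a 30-percentage-point difference in a therapy worth 1.0 HbA1c point: 0.30 × 1.0 = 0.3.

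| n per group | SD | SE | b/SE | False-positive rate |
|---|---|---|---|---|
| 50 | 1.5 | 0.300 | 1.00 | 17% |
| 50 | 2.0 | 0.400 | 0.75 | 12% |
| 50 | 2.5 | 0.500 | 0.60 | 9% |
| 42 | 1.5 | 0.327 | 0.92 | 15% |
| 42 | 2.0 | 0.436 | 0.69 | 11% |
| 42 | 2.5 | 0.546 | 0.55 | 9% |

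The 50 is the SAP's planned number, and 42 is the intervention count in its secondary analysis. The number of matched pairs is not stated.

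The opposite sign costs power. At n = 50 and SD 2.0, a true benefit of 1.12 points is detectable with 80% power. With b = −0.3 the apparent benefit is 1.12 − 0.3 = 0.82, and 0.82/0.4 = 2.05. P(Z > 1.96 − 2.05) is then about 54%.

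The bias equals b at any sample size.

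**The case against.** The Protocol states openly that the design is non-randomised with a retrospective control, so some confounding by period is a known limitation. Baseline HbA1c, the strongest obvious factor, is matched. Nothing in the documents shows that prescribing differed between periods. For scale, the difference detectable with 80% power at 50 per group is 0.84 to 1.40 points over the same assumed SDs, so a bias of a few tenths is modest. The control data set may not hold regimens. All of this stands. It limits the point to an unmeasured factor of unknown size, but it does not explain why an available correlate of HbA1c was left out.

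Several stronger readings are tempting and are not supported:

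- A reader might infer that the omission favours TREAT-ON. The documents show no change in drug practice and no direction.
- A reader might infer that medication was never recorded. The Protocol says that current therapy was reviewed at the TREAT-ON assessment, and the SAP does not list every baseline characteristic tabulated. Regimen is only not listed as an outcome or matching factor.
- A reader might see a period mismatch in the sentence "The DSMES sessions were in keeping with the assessment and content presented in the National Standards for DSMES", which carries a 2022 citation although the programme is cited to a 2019 report. It concerns educational content, in a past-tense account dated 2023, and does not date the controls.
- A reader might assume that 10 to 30 percentage points more patients start a drug class worth 0.7 to 1.2 points, giving 0.10 × 0.7 = 0.07 to 0.30 × 1.2 = 0.36, and take that as what regimen matching would remove. Those are starts during follow-up, which matching on baseline regimen would not remove.

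**Conclusion.** The point holds as a weakness of the primary contrast that should be addressed. Three facts in the documents carry it: the controls are past participants, medication recommendations belong to both programmes, and neither the propensity score nor the matched model is described as containing glucose-lowering therapy. The bias could run either way, and its size is not known. The rates of 9% to 17% show only what a 0.3-point imbalance would do under the stated assumptions, and they are not an estimate for this trial.

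Measuring baseline regimen would reduce one part of the problem. The period part stays with the design and has to be carried in the wording of the conclusion.

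**What to change.** 1. Confirm whether the control data set, or medical records linked to it, hold baseline regimen. For both arms extract insulin use (yes/no) and number of non-insulin glucose-lowering agents.
2. Add both to the propensity score, keep the caliper, and apply the same <0.1 standardised-difference check. The documents are written as if the matching has been done. If so, report the re-matched result as a labelled sensitivity analysis beside the a priori one.
3. If control regimens cannot be obtained, say so and report a sensitivity analysis for unmeasured confounding, for example the combinations of regimen imbalance and HbA1c effect that would move the confidence limit to zero.
4. Report the calendar windows of both groups.
5. Where available, tabulate new drug-class starts during follow-up by arm as description only. They are partly mediators, since both programmes recommend medication, so they should not be adjusted for.
6. State the conclusion as programme plus period, with no rule for lifting that caveat. A flat start-date trend among controls cannot exclude a change between the last control and TREAT-ON, and a small pool may look flat for lack of power.

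The cost is extraction of a few fields and one further matching run. Some pairs may be lost. How many cannot be said, because the size of the control pool is not given.

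### Does the SAP need to say how many TREAT-ON participants the caliper left unmatched, and what n=42 counts?

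*SAP*

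**What the plan says.** All of this is in the SAP, Statistical Analysis, unless noted.

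- **Planned size.** "We expected to enroll 50 participants into the intervention", to be compared with a "retrospective usual care group (control) that was also anticipated to include 50 participants". The controls come from an existing data set of earlier programme participants.
- **Matching.** "Propensity score matching was used to form pairs of intervention and control participants". The procedure is greedy, with a caliper of 0.2 SD of the logit of the propensity score, and "the closest control participant within the specified caliper distance was selected for matching". Six covariates enter the score: race, ethnicity, age, BMI, baseline HbA1c and gender.
- **Primary model.** HbA1c over time is analysed by mixed model. The covariates are left out of the propensity-matched model, with the reason "Since the baseline characteristics achieved a good balance".
- **Secondary analysis.** Participants who met their self-management goal are compared with those who did not, "using only the participants in the intervention group (n=42").
- **Purpose and outcome.** The Protocol's opening section says "The purpose of this study was to compare TREAT-ON, an enhanced telehealth version of the" earlier programme, with matched controls who had completed that programme in person. Under Outcome Measures, "HbA1c served as the primary outcome and clinical measure of improved DM management".

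Neither document gives the number enrolled, the number of pairs, the number unmatched or the number of eligible controls.

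**The concern.** A caliper limits the treated group as well as the controls: a TREAT-ON participant with no control in range leaves the comparison. The SAP is written in the past tense and reports that balance was reached, so the matching had been done and the counts existed. Yet the only achieved number is 42, and its meaning is open.

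- If 42 is everyone enrolled, the primary comparison rests on an unstated number of pairs, up to 42.
- If 42 is the matched group, the goal-met analysis, which needs no controls, may have left out unmatched TREAT-ON participants.
- If 42 is those with goal data, it says nothing direct about the number of pairs.

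What would be at stake is who the primary result applies to, and its precision. Balance is judged among those retained, so the statement of good balance does not show who was left out. If the groups differed at baseline, those left out would not be a random subset.

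**Working it through.** **1. The plan's own figure.** The SAP gives 50 per group without an effect size, SD, power or dropout rate, so it cannot be reproduced. Solving backwards (two-sided 5% test assumed, independent groups, one time point), the effect detectable with 80% power is (1.960 + 0.842) × sqrt(2/50) = 0.56 SD. The shortfall to the reported number is 50 − 42 = 8, or 8/50 = 16%. The documents do not attribute it: it could be under-enrolment, the caliper or missing data.

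**2. Is the analysed population stated?** Yes. The SAP forms pairs, selects one closest control for each intervention participant, and names its HbA1c model as the propensity-matched one. With one-to-one pairs, the number of pairs cannot exceed 42 if 42 is the enrolled or the matched group. Leaving out a participant with no control in range is what a caliper means, so an analyst needs no further rule.

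**3. What does n=42 most naturally mean?** The SAP restricts the secondary analysis to the intervention group, as opposed to controls, and puts 42 beside that group. The word matched does not appear there. The plain reading is the whole intervention group. The reading under which the goal-met analysis lost unmatched participants is possible, but nothing in the text supports it.

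**4. How many might the caliper remove?** This depends on the size of the control pool, which the documents do not give. The settings below are assumptions: 42 participants, one-to-one greedy matching without replacement, a caliper of 0.2 SD of the logit, the six SAP covariates, 1,200 runs per setting, and four set-ups differing in covariate distribution, matching order and SD definition. The assumed shift is age −3 years, BMI +1, HbA1c −0.4 and non-white +4 percentage points.

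| Controls available | Mean pairs, no shift | Mean pairs, assumed shift |
|---|---|---|
| 50 | 32.8–36.4 | 29.7–34.1 |
| 75 | 37.7–39.3 | 34.7–37.7 |
| 100 | 39.5–40.2 | 37.0–39.2 |
| 200 | 41.2–41.3 | 40.0–40.8 |

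The 50-control row looks worst, but it is poorly supported. The SAP's 50 is the anticipated size of the control group, and that group was then selected from earlier programme participants. It reads as the selected group, not the pool.

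With 50 controls and the assumed shift (one covariate set, random order), those left out had baseline HbA1c 0.68 points lower and were 5.2 years younger than those matched. Without the shift the differences were +0.04 points and +0.2 years. The apparent selectivity is thus produced by the assumed shift.

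**5. What would fewer pairs cost?** Half-width of the 95% interval for a difference in HbA1c change = t(0.975, 2m − 2) × SD × sqrt(2/m), for m pairs treated as independent groups at one time point and an assumed SD of 1.5 to 2.2.

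| m | t | sqrt(2/m) | SD 1.5 | SD 2.2 |
|---|---|---|---|---|
| 42 | 1.989 | 0.2182 | 0.651 | 0.955 |
| 36 | 1.994 | 0.2357 | 0.705 | 1.034 |
| 30 | 2.002 | 0.2582 | 0.775 | 1.137 |

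From 42 to 36 pairs the half-width grows by 0.705 − 0.651 = 0.054 to 1.034 − 0.955 = 0.079 points. From 42 to 30 it grows by 0.124 to 0.182. The assumed SD range alone moves it by 0.955 − 0.651 = 0.304 at 42 pairs. On the power scale, at the 0.56 SD effect of step 1, the figures are 72.8% with 42 pairs, 66.2% with 36 and 58.3% with 30. Whatever the number of pairs, a reported interval would already reflect it.

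**The case for a change.** The strongest case for acting is that the counts existed when the SAP was written, giving them would take one line, and without them a reader of these two documents cannot say whether the HbA1c result covers all TREAT-ON participants or only those who resemble past in-person participants. That is factually right: the numbers are absent and n=42 is undefined. With 50 enrolled and 75 controls, the simulations gave mean pairs of 39.9 to 46.0, so 42 could also be a matched count.

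What stands is a gap in reporting. It does not become a fault in the analysis, because enrolled, matched and unmatched counts are outcomes of running the matching. Their usual place is the participant flow and baseline table of the results, which are not among these documents. Supplying them would change no estimate, model or population.

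A weighted analysis that keeps everyone, such as overlap weights, might seem the natural remedy. In simulation it lowered the standard error by 9–16% against unadjusted matching with 50 controls. But it targets the overlap population and gives little weight to the poorly overlapping participants at issue, so it would not show what happened to all TREAT-ON participants. It would also be a post hoc addition beside a valid method. Directing the goal-met analysis to all enrolled participants would correct a defect that has not been shown.

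**Conclusion.** No change to the plan. The SAP leaves out the number enrolled, paired and unmatched and the number of eligible controls, and it does not define n=42. It does state the method and the population of the primary comparison: one-to-one matched pairs, at most 42 if 42 is the enrolled or the matched group. The documents do not show that the caliper removed anyone.

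The possible size runs from one or two participants with a pool of 200 to about 6 to 12 of 42 with a pool of 50. Both figures rest on assumed covariates, assumed shifts and matching without replacement, which is the natural reading of pairs but is not stated. The cost in precision is 0.05 to 0.08 HbA1c points of half-width at 36 pairs and 0.12 to 0.18 at 30, for an assumed SD of 1.5 to 2.2 and a single time point.

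This is a gap that analysts fill in the ordinary course of reporting. Someone reading the results should look there for the pair count and the meaning of 42 before generalising the HbA1c finding to every TREAT-ON participant.
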